10.3 Stratification Factors

Participants will be studied in separate strata. Stratum 1 will first enroll participants with lymphocyte T CD4+ count above 200/mm³. After Stratum 1 single agent therapy completes, Stratum 2 will enroll participants with lymphocyte T CD4+ count between 100-200/mm³. Stratum 2 will be evaluated starting at the single agent therapy MTD determined in Stratum 1, after reviewing the safety profile for Stratum 1. Stratum 2 participants will not be allowed to escalate beyond the MTD for Stratum 1; one dose level de-escalation will be allowed based on the doses in the schema in the treatment plan.

10.4 Analysis of Secondary Endpoints

10.4.1 Preliminary objective response rates

The proportion of participants achieving ORs (by RECIST criteria or KS response criteria, which includes RECIST for visceral disease, or by RECIL for cHL) and their corresponding 95% confidence intervals (calculated using exact Binomial) will be reported separately for solid tumor and cHL according to treatment (combination therapy and single agent) using response criteria designated in Section 9.0. Participants in the expansion cohort and those treated at any Dose Level in the dose de-escalation cohorts will be included. Disease-specific outcomes will be estimated for histologies with > 5 participants. For participants who fail therapy, the proportion with loco-regional vs. distant progression will be summarized. Descriptive statistics will also be compiled for DOR.

10.4.2 Immune function and other parameters

Descriptive statistics will be generated to evaluate the effects of single agent nivolumab, and the combination of ipilimumab and nivolumab, on immune function (HIV viral load, CD4 and CD8 cells).

Depending on the number of dose levels tested, immune status and HIV viral load will be summarized overall and according to dose level at pre-study and end of study. In an explorative fashion, change in these parameters from pre-study to the end of study will be examined using a nonparametric Wilcoxon signed-rank test.

Due to the small number of participants, no adjustments for multiple testing are planned.

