1.2 Secondary Objectives

- 1.2.1 Dose De-Escalation Cohort: To evaluate the effects of single agent nivolumab, and the combination of ipilimumab and nivolumab, on immune function (HIV viral load in plasma using conventional assay, CD4+, and CD8+ cells).
- 1.2.2 Solid Tumor Dose Expansion and cHL Cohorts: To preliminarily assess objective response rates associated with treatment for commonly represented solid tumors (Kaposi Sarcoma, anal cancer, and lung cancer) and relapsed refractory HIV-cHL.
- 1.2.3 Solid Tumor Dose Expansion and cHL Cohorts: To evaluate the effects of single agent nivolumab, and the combination of ipilimumab and nivolumab, on immune function (HIV viral load in plasma using conventional HIV assay, CD4+, and CD8+ cells). Only single agent nivolumab will be utilized in the cHL cohort.

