4.6.2 Other medications

Participants MUST receive medically appropriate care and treatment for HIV infection, including antiretroviral medications when clinically indicated. Suspension or modification of an antiretroviral regimen during study participation will be permitted (after 8 weeks from study entry) at the discretion of the physician providing HIV care, provided the change and its rationale are carefully documented.

Recommended prophylaxis for opportunistic infections is listed in Appendix VIII. Participants must be instructed to inform the investigators of the current or planned use or all other medications during the study (including prescription medications, over-the-counter medications, vitamins, and herbal and nutritional supplements). It is the responsibility of the investigator to ensure that details regarding all medications are documented. Only prescription medications will be recorded in the case report forms. Bisphosphonates started prior to screening activities or initiated during the course of the study to control bone pain may be used with caution.

As the study will identify DLTs of this treatment regimen during the initial cycle of therapy, prophylactic growth factor (G-CSF) administration is not recommended. Based on observed toxicities, protocol-specified dose modification guidelines should be followed for subsequent therapy cycles. Management of anemia will be at the discretion of the treating physician. No concurrent investigational agents are permitted.

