8.5.1 Review of medical history since last visit

- 8.5.2 Physical examination (vital signs, weight, performance status)
- 8.5.3 Review of changes in concurrent medications
- 8.5.4 Laboratory studies (as defined in Section 8.1.5)
 - a) CBC with differential and platelet count within 2 days prior to treatment
 - b) Serum chemistries (odd # cycles only 5, 7, 9, etc.)
 - c) Serum amylase and lipase (odd # cycles only 5, 7, 9, etc.)
 - d) Serum or urine pregnancy test for WOCBP at Cycle 5 Day 1 and every 12 weeks thereafter
 - e) HIV viral load and CD4/CD8 count at Cycle 5 Day 1 and every 12 weeks thereafter: Viral load studies will be performed using an assay with a limit of detection of 75 copies/ml or less. Repeat Hepatitis B antigen and/or Hepatitis C antibody if positive at baseline.
 - f) Immunologic labs at Cycle 5 Day 1 and every 12 weeks thereafter after consisting of: rheumatoid factor, C-reactive protein, ANA, SPEP, immunoglobulins, and free light chains (FLC).
 - g) Endocrine labs at Cycle 5 Day 1 and every 12 weeks thereafter consisting of: TSH, free T4, TPO, morning ACTH, and morning cortisol if ACTH is abnormal
- 8.5.5 AE assessment
- 8.5.6 Biological sample submissions for correlative studies. Samples will be collected as defined in Section 8.1.10, unless otherwise noted.
 - a) Collect two 6 ml red top tubes for assessment of circulating levels of proinflammatory molecules before cycle 5. Collection, shipping, and storage methods are described in Appendix XV.
 - b) Collect 2x2 mm biopsies in RNALater and formalin before cycle 5 as described in Appendix XIV (optional for KS cases only, with participant consent).
 - c) Collect anal swabs before cycle 5 as described in Appendix XVII (optional for anal cancer cases only, with participant consent).

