8.7 Treatment Discontinuation Evaluations

End of study assessments will be done at 6 weeks (\pm 1 week) and at 16 weeks (\pm 1 week) of the last dose of study treatment, unless otherwise noted.

Participants with ongoing toxicities should be seen more often as clinically indicated. The schedule of clinical follow-up for these participants will be at the discretion of the treating physicians and according to established Standard of Care. AEs Assessment on the study, including assessment of immune-mediated AEs and SAEs, will continue for all participants until 90 days after the last study drug administration.

- 8.6.1 Review of medical history since last visit
- 8.6.2 Physical examination (vital signs, weight, performance status)
- 8.6.3 Review of changes in concurrent medications
- 8.6.4 Laboratory studies (as defined in Section 8.1.5)
 - a) CBC with differential and platelet count
 - b) Serum chemistries
 - c) Serum amylase and lipase
 - d) Serum or urine pregnancy test for WOCBP

- e) HIV viral load, performed using an assay with a limit of detection of 75 copies/ml or less, CD4/CD8, and repeat Hepatitis B antigen and/or Hepatitis C antibody if positive at baseline
- f) Immunologic labs consisting of rheumatoid factor, C-reactive protein, and ANA
- g) Endocrine labs consisting of: TSH, free T4, TPO, morning ACTH, and morning cortisol if ACTH is abnormal
- h) For participants with HIV-cHL and with bone marrow involvement at screening, a bone marrow biopsy will be required to confirm complete remission.
- 8.6.5 AE assessment
- 8.6.6 Biological sample submissions for correlative studies (as defined in Section 8.1.10), within 6 weeks (\pm 1 week) of the last dose of study treatment only
 - a) Collect two 6 ml red top tubes for assessment of circulating levels of proinflammatory molecules (Appendix XV).
 - b) The collection, shipping, and storage of 2x2 mm biopsies in RNALater and formalin is described in Appendix XIV (optional for KS cases only, with participant consent).
 - c) The collection, shipping, and storage of anal swabs is described in Appendix XVII (optional for anal cancer cases only, with participant consent).
 - d) Blood draw: Twelve 8.5mL ACD tubes for assays (HIV DNA, HIV RNA, SCA, and Pheno/ICS) for all participants who consent to this optional draw with hematocrit ≥ 25. *These tubes will be shipped directly to the* AMC Biorepository *for processing* (Appendix XVI).

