10.5 Exploratory Objectives

All exploratory objectives will addressed in batch at the completion of enrollment/study as applicable. Some measures are only applicable to disease subsets.

- 10.5.1 Understand the immune response to agent in the context of ART, of altered immune function, and repertoire due to prior HIV infection
 - 10.5.1.1 To evaluate the effects of single agent nivolumab, and the combination of ipilimumab and nivolumab, on intratumor immune cells by IHC such as PD1, PDL-1, and others.
 - 10.5.1.2 To evaluate the effects of single agent nivolumab, and the combination of ipilimumab and nivolumab on circulating cytokine markers by multiplex assay.

- 10.5.2 To understand the response of human tumor viruses (HPV, EBV, and KSHV) to agent
 - 10.5.2.1 To evaluate the effects of single agent nivolumab, and the combination of ipilimumab and nivolumab on herpesvirus loads (EBV, KSHV, CMV) in plasma.
 - 10.5.2.2 To evaluate the effects of single agent nivolumab, and the combination of ipilimumab and nivolumab on latent herpesvirus (EBV, KSHV, CMV) in PBMC.
 - 10.5.2.3 To evaluate the effects of single agent nivolumab, and the combination of ipilimumab and nivolumab on herpesvirus specific CD8 and CD4 T cells in PBMC
 - 10.5.2.4 In cases of KS, to evaluate the effects of single agent nivolumab, and the combination of ipilimumab and nivolumab on viral transcription in tumor biopsies.
 - 10.5.2.5 In cases of anal cancer, to evaluate the effects of single agent nivolumab, and the combination of ipilimumab and nivolumab on HPV types in anal swabs, when feasible.
- 10.5.3 Understand the response of HIV to agent
 - 10.5.3.1. To evaluate the effects of single agent nivolumab, and the combination of ipilimumab and nivolumab on latent HIV loads in PBMC using outgrowth assay.
 - 10.5.3.2. To evaluate the effects of single agent nivolumab, and the combination of ipilimumab and nivolumab on HIV reactive T cells.
 - 10.5.3.3. Descriptive statistics will be generated for the above measures. Changes from pre-study to end of study will be explored using nonparametric Wilcoxon signed-rank test.

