- j. Scans will be performed at baseline, before cycle 5, and thereafter every 12 weeks. It is critical that all imaging studies or CT scans be performed in an identical way to the baseline scan with the same scanner, same scan direction, and consistent arm pointing. Confirmatory scans should also be obtained 4 weeks following initial documentation of objective response. If tumor flare is suspected, the participant must undergo a second scan within a month of the first scan and the case must be discussed with the principal investigator. If progression is documented at that time, participant must come off study. If a participant has a history of brain metastasis, a brain MRI at baseline is required. Participants with KS will be evaluated for response before odd numbered cycles (5, 7, 9, etc.). Scans will not be required for participants with KS unless clinically indicated.
 - For participants with relapsed refractory HIV-cHL, F-FDG-PET /CT scans will be done at baseline, and weeks 17 and 25. At week 49, an F-FDG-PET/CT scan is required for patients who did not have two consecutive negative scans before this time point. If F-FDG-PET/CT scans are done without contrast, a full scan with and without contrast will be required unless there is an allergy to IV contrast. CT with and without contrast will follow the same schedule as stated above. For patients with bone marrow involvement at screening, a bone marrow biopsy was required to confirm complete remission.
- k. Participants with ongoing toxicities should be seen more often as clinically indicated. AEs Assessment on the study will continue for all participants until 90 days after the last study drug administration. End of Study Assessment will be done within 6 weeks (±1 week) and at 16 weeks (±1 week) of the last dose of study treatment.
- 1. For participants with KS, tumor assessments with photographic record must be performed within 7 days prior to initiating treatment. Tumor assessments and photographs should be performed as outlined in the AMC Kaposi's Sarcoma (KS) Tumor Assessment MOP. KS tumor assessment will occur every 4 weeks during study participation.
- m. For participants with classical HL who had bone marrow involvement at baseline only.

Biological Sample Submissions for Correlative Studies

Specimens are to be submitted as outlined in Section 8. All samples will be submitted to the AMC Biorepository unless noted otherwise. All blood tubes are to be filled completely.

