- 9. Samples are to be collected within 6 weeks (± 1 week) of the last dose of study treatment only.
- 10. For dose levels 1 (including 240 mg q 2 weeks) and 2 only.

Schedule of Evaluations for participants on combination therapy solid tumor expansion cohort

				Cycles 1	-4						
Tests and Observations	Pre- Study	64	64	62	60	64		5-13, Day 1	Cycles 14-22	Off Study ^k	
Tests and Observations	Visit -1	t-1 D1 D8 D1 D1 D1 C5 7 0 11 Even cycles		Even cycles (6, 8, 10, 12)	cycles						
Informed consent	X										
Medical History, Physical Exam, PPD ¹ , Vital Signs, Weight, Performance Status ^{b,c}	X	X	X	X	X	X	X	X	X	X	
Height	X										
AE Assessment ⁱ	X	X	X	X	X	X	X	X	X	X	
Concurrent meds	X										
EKG ⁷	X										
Laboratory Studies ^b											
CBC w/diff, plts a, d	X	X	X	X	X	X	X	X	X	X	
Serum chemistry e	X	X	X	X	X	X	X		X	X	
Amylase/Lipase	X	X	X	X	X	X	X		X	X	
HBV, HCV ^f	X						В	efore Cycle 5 and th	en every 12 weeks	X	
Serum or Urine Pregnancy Test ^e	X	X		X	X	X	В	efore Cycle 5 and th	en every 12 weeks	X	
HIV viral load ^f and CD4/CD8 count	X						В	efore Cycle 5 and th	en every 12 weeks	X	
Immunologic Labsg	X						В	efore Cycle 5 and th	en every 12 weeks	X	
Endocrine Labsh	X						В	efore Cycle 5 and th	en every 12 weeks	X	
Radiologic Evaluation/ Response Assessment ^j	X						В	X			
KS Tumor Assessment ¹	X				X		X		X	X	
ACSR Donation (optional with consent)	X						See Appendix IV				

Therapeutic Parameters

- 1. Prestudy PPD testing (only if known to be negative) is only required within the last 12 weeks before enrollment. The Quantiferon assay is an acceptable alternative to PPD testing. If PPD positive, prophylaxis must be complete before enrollment.
- 2. Prestudy scans and x-rays used to assess all measurable or non-measurable sites of disease must be done ≤ 4 weeks prior to registration.
- 3. Prestudy CBC (with differential and platelet count) should be done ≤ 2 weeks prior to registration.
- 4. All required prestudy chemistries, as outlined in Section 8.1.5, should be done ≤ 2 weeks prior to registration unless specifically required within 48 hours before starting treatment as per protocol.
- 5. Baseline Hepatitis B and C testing and viral load studies (HIV, if indicated Hepatitis B and C studies) should be done ≤ 2 weeks prior to registration.
- 6. See Table below regarding biologic sample submissions.

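### Viral load and CD4/CD8 are tested only from pre-study to an off-treatment visit, so no scheduled on-treatment value enters a named test

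*Combined protocol and SAP*

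**What the plan says.** Section 1.2 makes viral load, CD4+ and CD8+ cells a secondary objective in the de-escalation, expansion and cHL cohorts: "To evaluate the effects of single agent nivolumab, and the combination of ipilimumab and nivolumab, on immune function".

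Section 10.4.2 opens with a promise of descriptive statistics and sets no time points for them. It then summarises immune status and viral load, overall and by dose level, at pre-study and end of study, and adds that "change in these parameters from pre-study to the end of study will be examined using a nonparametric Wilcoxon signed-rank test". It calls this explorative. Section 10.5.3.3 repeats the contrast for exploratory measures: "Changes from pre-study to end of study will be explored using nonparametric Wilcoxon signed-rank test".

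The end-of-study visits come after treatment. Section 8.7 begins "End of study assessments will be done at 6 weeks" and adds a second visit at 16 weeks, both counted from the last dose. Appendix I note k words the first visit slightly differently ("End of Study Assessment will be done within 6 weeks"). Viral load and CD4/CD8 are listed for these assessments without limiting them to one visit. The off-study correlative samples, cytokines included, belong to the 6-week window "of the last dose of study treatment only" (Appendix I, biological samples, note 9).

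On treatment, Section 8.5.4 schedules "HIV viral load and CD4/CD8 count at Cycle 5 Day 1 and every 12 weeks thereafter". Cytokines are drawn once on treatment, before Cycle 5 (Section 8.5.6; Appendix XV, 4.0).

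**The concern.** The objective asks what treatment does to viral load and CD4/CD8. The only named contrast compares a value before treatment with one taken weeks after treatment ends.

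Entry requires a suppressed viral load (Section 3.1.9), so the change that could appear is a rise. The protocol also provides for that rise to be treated. Section 4.6.1 advises an ART change above a confirmed 1,000 copies, and Section 4.6.2 permits regimen changes once 8 weeks have passed since entry, about when the first on-treatment value is drawn. A rise that is found and brought back down before the tested visit leaves a paired difference of zero or close to it. Followed to the letter, the plan could report no change after real on-treatment rebounds.

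Appendix XV expects cytokines to rise after treatment starts and to fall after it ends. A comparison of baseline with the off-study sample skips the time point at which the rise is expected.

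**Working it through.** The plan attaches no alpha, power or sample size to these tests, so there is no figure of its own to reproduce. Steps 1 to 3 use protocol inputs; steps 4 to 6 are illustrations under assumed values.

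**1. On-treatment values in no named test.** Cycles last 2 weeks. Cycle 5, then every 12 weeks (6 cycles), up to Cycle 46 gives cycles 5, 11, 17, 23, 29, 35 and 41: 7 values, at weeks 8, 20, 32, 44, 56, 68 and 80 after the first dose. A participant who stops before Cycle 5 has 0; last cycle 5–10 gives 1, 11–16 gives 2, 17–22 gives 3.

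**2. Time for a Cycle 5 rise to be suppressed again.** With last cycle L, weeks from Cycle 5 Day 1 to the tested visit = 2 × (L − 5) + 6, or + 16:

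| Last cycle | To 6-week visit | To 16-week visit |
|---|---|---|
| 5 | 6 | 16 |
| 11 | 18 | 28 |
| 23 | 42 | 52 |
| 46 | 88 | 98 |

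**3. Why the unchosen visit matters.** Section 2.2.1 gives a nivolumab half-life of 17 to 25 days. Assuming simple exponential decay, the fraction left is 2^(−t/half-life): 18% to 31% at 42 days and 1.0% to 4.5% at 112 days. The two visits measure different states.

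**4. Rebound (assumed counts).** Suppose 8 of 24 participants rebound on treatment: 33%, exact (Clopper-Pearson) 95% CI 15.6% to 55.3%. If values below 75 copies/mL are treated as tied, the signed-rank test uses only participants still detectable at the tested visit. With k of them, all rising, the exact two-sided p is 2/2^k: k = 5 (5/24 = 21%) gives 0.0625, k = 6 gives 0.031, and k = 0 leaves nothing to test. Conversely, no rebounds at all would bound the rate at 1 − 0.025^(1/n): 26.5% (n = 12), 17.6% (n = 19) or 14.2% (n = 24).

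**5. Number of tests.** With independent tests and a chance p per test of a value ≥75, the chance of at least one is 1 − (1 − p)^k:

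| p | 1 test | 3 tests | 7 tests |
|---|---|---|---|
| 2% | 2% | 6% | 13% |
| 5% | 5% | 14% | 30% |
| 10% | 10% | 27% | 52% |

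A rebound proportion therefore needs the number of tests per participant beside it.

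**6. Cytokines (assumed effect, dropout and persistence).** Suppose 24 are enrolled, 19 reach Cycle 5 and all 24 give an off-study sample. Exact signed-rank power, two-sided 5%, normal paired changes, 200,000 simulated data sets (runs of a few thousand differ by up to about 2 points):

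| Rise (SD of paired change) | Cycle 5, n = 19 | Off study, n = 24: 100% persists | 50% | 25% | 0% |
|---|---|---|---|---|---|
| 0.8 | 90% | 96% | 45% | 15% | 5% |
| 0.5 | 52% | 63% | 21% | 9% | 5% |

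At 0.8 SD the two contrasts break even when roughly 87% of the rise persists. The documents give no persistence figure.

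**The case against.** **Adverse-event reporting would catch the rebound.** A reader might infer that a suppressed rebound would go unrecorded. The documents do not support that. Section 6.4.1 makes an abnormal result clinically significant if it meets any listed criterion, therapeutic intervention among them, and significant results are reported as adverse events. A rise that leads to an ART change would usually qualify, and Section 10.1.2 tabulates toxicity with all treated participants evaluable. What remains is that significance rests on the investigator's judgement, no viral-load threshold is set, and no rebound proportion results.

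**On-treatment viral change is already an aim.** Section 2.4.9 plans single-copy and cell-associated RNA measurements to look for reactivation, with on-treatment samples. That shows the question was not overlooked. But no test is named there, and Section 2.4 says that, unless otherwise noted, specimens are stored until funding is available.

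**The Cycle 5 cytokine value is planned for use.** A reader might infer that the cytokine hypothesis will go untested. That is too strong: Appendix XV, 1.0 lists Cycle 5 among its time points, and 5.0 says the hypothesis will be tested. Only the test is unnamed. Section 10.5.3.3 covers cytokines only if its reference to the measures above means all of 10.5. If so, its contrast skips Cycle 5; if not, Section 10 names no cytokine test.

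**Off treatment is not drug-free.** Correct at 6 weeks, as step 3 shows. That strengthens the case for naming the visit.

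**Descriptive statistics are open-ended, and the analyses are exploratory.** Both are true. On-treatment summaries are allowed, but none is named.

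**Conclusion.** The point holds for viral load and CD4/CD8: one named contrast, an off-treatment endpoint with the visit unchosen, and up to 7 scheduled on-treatment values per participant outside any named test. For cytokines it holds in a narrower form: the Cycle 5 comparison is planned but has no named test.

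The schedule counts and intervals in steps 1 and 2 follow from the protocol. The drug fractions in step 3 add an assumption of simple decay. The rebound counts, per-test rates, effect sizes, dropout and persistence are assumed and measure no actual loss; the p-value floor also depends on the tie rule proposed here. It would be wrong to read the figures as showing that the present contrast is always weaker: if a cytokine rise persists fully, that contrast has more power.

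No DLT or MTD decision is affected. The change should be made because a secondary objective in every cohort could otherwise be answered with a comparison that misses what happened on treatment.

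**What to change.** Amend Sections 10.4.2 and 10.5, keeping everything exploratory:

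1. Among participants with at least one post-baseline on-treatment viral load, report the number and proportion (exact 95% CI) with any on-treatment value ≥75 copies/mL and, separately, with >1,000 on two consecutive readings. State how many participants have no on-treatment value and how many tests each had. The cut-offs come from Sections 3.1.9 and 5.1 and serve the analysis only; no clinical rule changes.
2. Treat all values below 75 copies/mL as one category at every visit, since assays need only a detection limit of 75 or less.
3. Name pre-study to pre-Cycle 5 as an exploratory signed-rank contrast for CD4, CD8 and cytokines, and Cycle 5 to the 6-week off-study visit for cytokines. Report how many stop before Cycle 5.
4. Summarise the 12-weekly CD4/CD8 and viral load values over time.
5. Keep pre-study to end of study as supportive, and state whether the 6- or 16-week visit supplies viral load and CD4/CD8.

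The cost is wording and a little more analysis; the visits and samples are already scheduled. There are three downsides. Participants who stop before Cycle 5 drop out of the Cycle 5 contrast. The ≥75 tally counts single transient elevations. For cytokines, the Cycle 5 contrast gives up some power if the rise fully persists off treatment, which is one reason to keep the present contrast.
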